7.4.3. Overall Response Rate in Follicular Lymphoma and Overall Populations

Overall response rate is defined as the proportion of participants who achieved a best overall response of CR or PR as determined per the Lugano classification (Cheson et al 2014) at any time during the study but before the first PD and before/at the start of a new antilymphoma treatment.

Overall response rate will be compared and analyzed in the same manner as described in Section 7.3.2.2 for PET-CR rate in the FDG-avid FL population.

Overall response rate will be analyzed for the FL population and the overall population. Overall response rate will also be analyzed in the MZL population.

7.4.4. Duration of Response in the Follicular Lymphoma and Overall Populations

Duration of response is defined as the time from first tumor response (CR or PR as per the Lugano classification [Cheson et al 2014]) until the time of first documented disease progression, or death from any cause, whichever is earlier, among participants who achieve an objective response (CR or PR as per the Lugano classification [Cheson et al 2014]). Censoring of DOR will follow the same algorithm as the censoring of PFS (see Section 7.3.1).

Kaplan-Meier estimation of the median DOR and its 95% CIs will be presented by treatment group for participants who achieve an objective response (CR or PR as per the Lugano classification [Cheson et al 2014]). No statistical comparison will be performed for this analysis.

Duration of response will be analyzed for the FL population and the overall population. Duration of response will also be analyzed for the MZL population.

7.4.5. Overall Survival in Overall Population

Overall survival in the overall population (FL and MZL) will be compared and analyzed in the same manner as described in Section 7.3.2.3 for the OS in the FL population. The only difference will be that the strata information for the stratified log-rank test will be based on the randomization factor used for both cohorts, FL and MZL: number of prior lines of therapy ($< 2 \text{ versus} \ge 2$).

7.4.6. Analysis of Efficacy Endpoints by Independent Review Committee

The endpoints PFS, ORR, and DOR, as determined by IRC assessment using International Working Group 2014 response criteria (Cheson et al 2014) will be analyzed in the FL, MZL, and overall populations. The above mentioned outcomes will be analyzed the same way as described for the respective efficacy endpoints by INV (Section 7.3.1, Section 7.4.3, and Section 7.4.4).

The response assessment concordance rate between INV assessment and IRC assessment will be evaluated in term of:

• Best overall response

The concordance rate is the number of concordant participants over the total number of assessed participants and will be calculated.

7.4.7. Quality of Life Questionnaires in Follicular Lymphoma and Overall Populations

Quality of life will be assessed using three questionnaires: the EORTC QLQ-C30, the EQ-5D-5L, and FACT-Lym tools.

7.4.7.1. **EORTC QLQ-C30**

The EORTC QLQ-C30 v3 is a 30-item scale (Aaronson et al 1993). The EORTC QLQ-C30 is composed of both multi-item scales and single-item measures. These include 5 functional scales, 3 symptom scales, a global health status scale, and 6 single items (see Table 7).

Global Quality of Life

All of the scales and single-item measures range in score from 0 to 100. A high scale score represents a higher response level. Therefore, a high score for a functional scale represents a high/healthy level of functioning and a high score for the global health status/QoL represents a high QoL. A high score for a symptom scale/item represents a high level of symptomatology/problems.

Scores will be calculated using the EORTC OLO-C30 scoring manual (third edition) as well as handling of missing data (Fayers et al 2001).

Descriptive statistics for each of the scores will be tabulated. The EORTC QLQ-C30 will be analyzed using change from baseline and percentage of change from baseline for each visit and treatment group in both FL and overall population, according to the functional scores and the recommendations in the EORTC scoring manual.

Statistical tests might be performed in an exploratory manner. Mann-Whitney tests for simple comparison and longitudinal data modeling techniques might be conducted to analyze the scores.

Functional Scales (15 Questions)	Symptom Scales (7 Questions)	Single Items (6 Questions)	
Physical (Items 1 to 5)	Fatigue (Items 10, 12, 18)	Constipation (Item 16)	

Table 7: **EORTC QLQ-C30 Scales**

(15 Questions)	(/ Questions)	(6 Questions)	(2 Questions)
Physical (Items 1 to 5)	Fatigue (Items 10, 12, 18)	Constipation (Item 16)	Global QoL (Items 29, 30)
Role (Items 6, 7)	Pain (Items 9, 19)	Diarrhea (Item 17)	-
Cognitive (Items 20, 25)	Nausea/Vomiting (Items 14, 15)	Sleep (Item 11)	-
Emotional (Items 21 to 24)	-	Dyspnea (Item 8)	-
Social (Items 26, 27)	-	Appetite (Item 13)	_
_	_	Financial (Item 28)	_

7.4.7.2. EO-5D-5L

The EQ-5D-5L is a 5-items questionnaire and a visual analogue scale ranging from 0 (worst imaginable health state) to 100 (best imaginable health state).

The 5 questions cover mobility, self-care, usual activities, pain/discomfort, and anxiety/depression and have 5 response levels: no problems, slight problems, moderate problems, severe problems, and unable to/extreme problems.

As described in the EQ-5D-5L manual (EuroQol 2019) descriptive statistics will be reported for the visual analogue scale. Change from baseline and percentage of change from baseline for each visit and treatment group in both FL and overall population will be analyzed as mentioned in Section 7.4.7.1.

The results from the 5 questions will analyzed as follows: the numbers and percentages in each of the 5 levels will be reported by treatment and visit as well as the presence of any severe to extreme problems (levels 4-5).

7.4.7.3. **FACT-Lym**

The FACT-Lymphoma (v4) is composed of 42 items with a 5-point Likert-type scale (Hlubocky et al 2013).

The questionnaire is composed of 5 subscales:

- Physical well-being sub-scale includes 7 items measured on 0- to 4-point scale: total score ranges from 0-28.
- Social/Family well-being sub-scale includes 7 items measured on 0-to 4-point scale: total score ranges from 0-28.
- Emotional well-being sub-scale includes 6 items measured on 0- to 4-point scale: total score ranges from 0-24.
- Functional well-being sub-scale includes 7 items measured on 0- to 4-point scale: total score ranges from 0-28.
- Lymphoma sub-scale includes 15 items, and scores range from 0 to 60.

The scoring will be performed following the official guideline (FACT-Lym Scoring 2005) as follows:

For each subscale:

- Reversals should be performed as indicated and individual items should be summed to obtain a score.
- The sum of the item scores should be multiplied by the number of items in the subscale, then divided by the number of items answered. This produces the subscale score.

Three total scores can be derived by adding the subscales as follows:

- FACT-Lymphoma Trial Outcome Index (TOI): (PWB score) + (FWB score) + (LymS score); total score ranges from 0-116.
- FACT-G total score: (PWB score) + (SWB score) + (EWB score) + (FWB score); total score ranges from 0-108.
- FACT-Lymphoma total score: (PWB score) + (SWB score) + (EWB score) + (FWB score) + (LymS score); total score ranges from 0-168.

The higher the score, the better the QoL.

Descriptive statistics will be reported for each of the subscales and the 3 total scores. Change from baseline and percentage of change from baseline for each visit and treatment group in both FL and overall population will be analyzed as mentioned in Section 7.4.7.1.

7.6. Sensitivity and Supportive Analyses for Efficacy Endpoints

The following sensitivity analysis may be performed:

- For time-to-event endpoints, the assumption of proportional hazard may be tested using a goodness-of-fit test based on Schoenfeld residuals (Kleinbaum and Klein 2012), and Schoenfeld residuals may be displayed graphically. In case the test reveals a significant deviation from the assumption of proportional hazards, weighted log-rank test (Zucker and Lakatos 1990), or RMST (Royston and Parmar 2013) may be performed.
- For time-to-event endpoints, an unstratified log-rank test may be performed and an unadjusted HR may be obtained using the unstratified Cox Proportional Hazard model.
- Stratification factors per IRT will be summarized: POD24 (yes versus no; FL only), refractoriness to prior anti-CD20 mAb therapy (yes versus no; FL only), the number of prior lines of therapy (< 2 versus ≥ 2). The number of participants with disagreement for each stratification factor between IRT and the eCRF will be summarized if any. Stratified analyses may be performed using stratification factors from the eCRF if at least 1 stratification factor per IRT and eCRF disagrees for at least 5% of the total randomized participants.
- For binary endpoints such as PET-CR rate and ORR, Fisher's exact test may be performed.
- For the primary and key secondary endpoint of PFS in the FL population and the overall population, the analysis may be performed considering participants having an event after 2 or more missed visits as having a PFS event. The censoring rule is the same as described in Section 7.3 for PFS, except for death or progression after 2 or more missed assessments, the outcome is progression, and date of death or progression will be used. The change in censoring rules is presented in Table 8.

Table 8: Change in Censoring Rules in Sensitivity Analysis Versus Primary Analysis of PFS When PD/Death After 2 or More Missed Assessments is Treated as PFS Event

Situation	Outcome as per Primary Analysis	Censoring Date as per Primary Analysis	Outcome as per Sensitivity Analysis	Date of Event as per Sensitivity Analysis
Death or progression after 2 or more missed assessments	Censored	Date of last adequate tumor assessment	Event	Date of progression/death

• For the primary and key secondary endpoint of PFS in the FL population and the overall population, the analysis will correct for potential bias in the follow-up schedules for disease assessment by assigning the dates for censoring and events only at scheduled visit dates. It is the same as the primary analysis described in Section 7.3 except that the date of progression is approximated as the date of the Protocol-scheduled visit immediately after the radiologic assessment of PD. The change in censoring rules is presented in Table 9.

Table 9: Change in Censoring Rules in Sensitivity Analysis Versus Primary Analysis of PFS When Protocol-Scheduled Visit is Used as the Date of Progression

Situation	Outcome as per Primary Analysis	Censoring Date as per Primary Analysis	Outcome as per Sensitivity Analysis	Date of Event as per Sensitivity Analysis
Progression documented between scheduled response assessments	Progressed	Date of first overall response of PD	Progressed	Date of next scheduled visit

• For the primary and secondary efficacy endpoints, sensitivity analyses may be performed to evaluate the impact of subsequent antilymphoma therapy. For the PFS and DOR endpoints, sensitivity analyses may be performed per EMA guidelines to consider new antilymphoma treatment as an event or consider all disease progressions and deaths as events regardless of whether they occur after initiating new antilymphoma treatment. Participants without an event observed should be censored at the last time known to be alive. The change in censoring rules is presented in Table 10 and Table 11.

Table 10: Change in Censoring Rules in Sensitivity Analysis Versus the Primary
Analysis of PFS When New Antilymphoma Treatment is Treated as an Event

Situation	Outcome as per Primary Analysis	Censoring Date as per Primary Analysis	Outcome as per Sensitivity Analysis	Date of Event as per Sensitivity Analysis
New antilymphoma treatment started	Censored	Date of last adequate tumor assessment with no documented progression (not NE and not missing) on/before starting a new antilymphoma treatment	Progressed	Date of new antilymphoma treatment

Table 11: Change in Censoring Rules in Sensitivity Analysis Versus the Primary Analysis of PFS When PD/Death is Treated as an Event Regardless of Initiation of New Antilymphoma Treatment

Situation	Outcome as per primary analysis	Censoring date as per primary analysis	Outcome as per sensitivity analysis	Date of event as per sensitivity analysis
New antilymphoma treatment started	Censored	Date of last adequate tumor assessment with no documented progression (not NE and not missing) on/before starting a new antilymphoma treatment	Not applicable	Not applicable

• As supportive analysis, treatment switch-adjusted OS might be performed to correct for the start of new antilymphoma treatment.

Additional sensitivity analysis may be conducted as needed.

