- Participants with negative PET scan at baseline should be followed using CT or MRI imaging. Additional PET scans may be performed at the treating investigator's discretion but are not required.
- Participants with a positive PET scan at baseline (FDG-avid lymphoma) who achieve radiologic CR during treatment should be assessed by PET scan within 4 weeks (± 2 weeks) of the CT/MRI scan, noting the CR to evaluate for metabolic response. Subsequent PET scans are not required if a confirmatory PET scan is performed during treatment; otherwise, a PET scan will need to be repeated at EOT.
- CT/MRI scans are to be performed according to the following schedule:
 - Year 1: Every 12 weeks (3 months, ± 2 weeks), including the EOT visit.
 Circumstances where scans cannot be performed at EOT (eg, due to hospitalization, hospice care, recent per-protocol scan, etc.) must be properly documented in the eCRF
 - Years 2 to 3: Every 16 weeks (4 months, \pm 2 weeks)
 - Years 4 to 6: Every 24 weeks (6 months, \pm 3 weeks)
- For CT/MRI scans reporting PD, a PET-CT or PET-MRI scan should be performed within 4 weeks (± 2 weeks) for confirmation of progression.

Response assessments using Lugano criteria (Cheson et al 2014) are to be performed each time lesions are assessed.

Participants who discontinue treatment for reasons other than disease progression will enter the efficacy follow-up period (see Section 8.9.2). Lesions must followed using the same modality and schedule as was used during the treatment period until progression of disease, initiation of new anticancer therapy, death, or withdrawal of consent.

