8.9.2. Efficacy Follow-Up

Participants who discontinue study treatment for reasons other than disease progression will continue to be assessed for efficacy (eg, scans performed at regular intervals) during this period. Participants will continue to be assessed at the intervals noted in Section 8.2.4 until disease progression, initiation of new anticancer therapy, lost to follow-up, withdrawal of consent, or death is reported. Participants with PD confirmed will move into the survival follow-up phase (see Section 8.9.3).

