7.3. Analysis of the Primary and Key Secondary Efficacy Endpoints

7.3.1. Primary Efficacy Analysis for Progression-Free Survival in Follicular Lymphoma

Progression-free survival by INV assessment is defined as the time from the date of randomization to the date of first documented disease progression, as determined by disease assessment per the Lugano classification (Cheson et al 2014) or death due to any cause, whichever occurs earlier. For the primary analysis, PFS will be censored if no PFS event is observed before the cutoff date or the date that a new antilymphoma therapy is started. Censoring for PFS will follow the algorithm outlined in Table 6, which is based on the FDA Guidance (FDA 2015, FDA 2018).

Table 6: Evaluation and Censoring of Progression-Free Survival

Situation	Date of Progression or Censoring	Outcome	Censoring Reason
No baseline tumor assessments	Date of randomization	Censored	No baseline assessment
No valid postbaseline response assessments	Date of randomization	Censored	No postbaseline assessment
Progression documented between scheduled response assessments	Date of first overall response of PD	Progressed	Not applicable
No progression	Date of last adequate tumor assessment (not NE and not missing) prior to cutoff date	Censored	Ongoing
Study discontinuation without documented progression	Date of last adequate tumor assessment (not NE and not missing) prior to cutoff date	Censored	Study discontinuation
New antilymphoma treatment started	Date of last adequate tumor assessment with no documented progression (not NE and not missing) on/before starting a new antilymphoma treatment	Censored	Start of new antilymphoma treatment
Death before first progressive response assessment	Date of death	Progressed	Not applicable
Death between adequate response assessments	Date of death	Progressed	Not applicable
Death or progression after 2 or more missed assessments	Date of last progression assessment with documented nonprogression	Censored	Death or PD after 2 or more missed assessments

The date of last adequate tumor assessment is the date of the last tumor assessment with an overall lesion response of CR, PR, or SD. In this case, the last tumor evaluation date at that assessment is used. If a PFS event is observed after a single missing or nonadequate tumor assessment, the actual date of event will be used, as per the Lugano classification (Cheson et al 2014).

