7.3.2.3. Overall Survival in the Follicular Lymphoma Population

Overall survival is defined as the time from randomization until death from any cause. All participants should be followed until death or until the end of study, whichever comes first, as specified in the Protocol.

The cause of death ("disease progression," "adverse event," or "other") will be summarized.

Participants who are not reported as a death at the time of the analysis cutoff will be censored at the earlier of the analysis cutoff and date of last known alive. The last known alive date is defined as the later of the last study visit and the date the participant was last known alive from the "Survival Follow-Up," "End of Treatment," and "End of Study" eCRFs. Partial death dates will be handled using the rules described in Section 4.1.4.

Overall survival will be compared and analyzed using stratified tests as described in Section 7.3 for PFS with FL in the FAS at the time of interim, primary, and final analysis. Participants will be censored at the last date they were known to be alive, regardless if a new antilymphoma therapy was started.

Post-treatment systemic antilymphoma therapies will be summarized and listed.

[figure not shown]

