10.2. Changes to the Statistical Analysis Plan

10.2.1. Amendment 1

The following clarifications have been added in the SAP:

- Table 1 was updated to align with Protocol Amendment 6.
- Section 7.3 was updated to clarify how to handle participants with confirmed diagnosis different to the one used for randomization.
- Section 7.3.2.1 and Section 7.4.5 were updated to clarify the stratification factors to be included in the analysis.
- Section 7.3.2.3 and Section 7.6 were updated to clarify the censoring rules for overall survival.
- Section 8.2.3 was added.
- Section 8.2.4 was updated to clarify the AE summaries.
- Appendix A was updated to reflect the additional tables/listings from Section 8.2.3 and the modification listed in Section 8.2.4.

In addition, other minor, administrative changes have been incorporated throughout the SAP and are noted in the redline version of the amendment.

10.2.2. Amendment 2

The following clarifications and modification have been added in the SAP:

- Table 1, Section 3.2, Section 7.3, and Section 7.4 were updated to align with Protocol Amendment 7.
- Section 3.2 was updated and Section 9.2 was added to describe an OS futility interim analysis to be performed at the time of the PFS primary analysis.
- Section 4.1.4 was updated to clarify how to handle a partial last prior therapy date.
- Section 4.2.2 was updated to clarify the definition of prior and concomitant medication in case of partial drug administration dates.
- Section 5.3 was updated to change the MRD evaluable set (to include the sample origin) and the FDG-avid population.
- Section 6.1.1 was updated to add COVID-19 vaccination status at screening to the analyzed baseline characteristics.
- Section 6.4 was updated to add the lenalidomide exposure table by creatinine clearance groups. Duration category for tafasitamab and lenalidomide were updated.
- Section 6.5.1 was updated to clarify the calculation.
- Section 7.4.2 was modified to clarify the origin of the MRD samples, the definition of sample stability, the threshold to be used to define negativity, and the denominator to calculate the MRD negativity rates.
- Section 7.4.6 was added to describe the IRC-related analysis.
- Section 7.4.7 was updated to clarify the analysis of the three quality of life questionnaire included in the study.
- Section 7.6 was updated to remove the option of running Renyi test as additional sensitivity analysis. This test was considered redundant with the other options proposed.

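### SAP 7.6 gives the optional EMA-type PFS and DOR sensitivity analyses the overall-survival censoring date, which confounds what they test and can inflate PFS and DOR

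*SAP*

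**What the plan says.** SAP 7.6 has a bullet on the effect of subsequent antilymphoma therapy. It opens with the primary and secondary efficacy endpoints in general, then narrows: "For the PFS and DOR endpoints, sensitivity analyses may be performed per EMA guidelines to consider new antilymphoma treatment as an event", or alternatively to count every progression and death whether or not new therapy came first. The next sentence is "Participants without an event observed should be censored at the last time known to be alive". The bullet then points to Tables 10 and 11, both titled as PFS analyses. Each table has one row, for participants who start new antilymphoma treatment.

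Elsewhere the plan uses another date. For a participant without progression, SAP 7.3.1 Table 6 gives "Date of last adequate tumor assessment (not NE and not missing) prior to cutoff date". SAP 7.4.4 applies the same algorithm to DOR. Last-known-alive appears in SAP 7.3.2.3, for OS: "Participants will be censored at the last date they were known to be alive, regardless if a new antilymphoma therapy was started". Protocol 10.4.1.6 describes the same two sensitivity analyses without any last-known-alive rule.

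On follow-up, Protocol 8.2.4 requires lesions to be followed "until progression of disease, initiation of new anticancer therapy, death, or withdrawal of consent", and Protocol 8.9.2 says much the same. Protocol 8.9.3 continues survival contact every 12 weeks.

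**The concern.** Contact that shows a participant is alive does not show that the lymphoma has not progressed. Required scans end at new anticancer therapy and survival contact does not, so the last-known-alive date can fall well after the last scan. Censoring PFS or DOR at that date keeps the participant in the risk set through time when no protocol-required scan could show progression.

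Two groups show the problem. Protocol 7.1.1.3 sends participants who need new therapy for insufficient response, without progression, straight to safety and survival follow-up. Table 6 censors participants with no valid postbaseline assessment at randomization, whereas the sentence in 7.6 would give them progression-free time up to last contact.

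Interpretation is also at stake. Of the PFS sensitivity analyses listed in SAP 7.6, only these two vary the handling of new therapy. If the censoring date of every event-free participant moves at the same time, a difference from the primary result has two possible causes, and agreement is not clean reassurance.

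**Working it through.** **1. Inputs, checked against the plan's own figure.** SAP 3.3 gives HR 0.65, 80% power, two-sided 5%, 1:1 allocation, medians of 27.8 (TGB) and 42.8 (TGA) months, 21 months of enrollment, 12 months of follow-up, 15% dropout, 174 events and 528 participants.
- Freedman: [(1.9600 + 0.8416) × (1 + 0.65)/(1 − 0.65)]² = (2.8016 × 1.65/0.35)² = 174.4. The plan states 174.
- Schoenfeld: 4 × 2.8016²/(ln 0.65)² = 169.2, so 170 events.
- Dropout: 448/0.85 = 527.1, so 528.

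The design inputs are therefore read correctly. They do not settle the censoring question.

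**2. The rules side by side.**

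| Analysis | Starts new therapy | No event |
|---|---|---|
| Primary PFS (Table 6) and DOR (7.4.4) | Censored at last adequate scan on or before the start | Last adequate scan |
| Table 10 | Event at therapy start | No row; text says last known alive |
| Table 11 | Not censored at therapy start | No row; text says last known alive |
| OS (7.3.2.3) | Ignored | Last known alive |

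The tables are meant to show what changes from the primary analysis. Their silence on event-free participants implies that Table 6 still applies, which contradicts the sentence above them.

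**3. Who is exposed.** In the Table 11 analysis: participants who start new therapy and stay at risk without required scans, plus those who stop scans for other reasons. In the Table 10 analysis, starting new therapy is itself the event, so only those who stop scans without new therapy are affected.

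**4. Size.** No closed formula applies, so the design was simulated.
- PFS was exponential with the SAP 3.3 medians, accrual 21 months, cutoff at month 33.
- Scans were every 12 weeks in year 1, 16 in years 2 to 3 and 24 in years 4 to 6 (Protocol 8.2.4). Survival contact was every 12 weeks.
- The death hazard came from the 120-month control median OS in SAP 9.2.1, multiplied by 0.65 in TGA.
- The share who stop scans without progression but stay in survival follow-up is an assumption, varied from 0% to 25%, with stop times uniform over 0 to 24 months.
- Each scenario used eight runs of 20,000 participants. Events and event dates were identical under both rules; only the censoring date of event-free participants differed.

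Kaplan-Meier PFS at about 24 months (evaluated at 24.5), last adequate scan → last known alive:

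| Share stopping scans | TGB % | TGA % | HR |
|---|---|---|---|
| 0% | 56.0 → 56.3 (+0.3) | 68.6 → 68.9 (+0.3) | 0.657 → 0.656 |
| 10% per arm | 55.4 → 57.7 (+2.3) | 68.5 → 70.3 (+1.8) | 0.650 → 0.650 |
| 25% per arm | 54.3 → 59.7 (+5.4) | 67.5 → 71.6 (+4.1) | 0.653 → 0.655 |
| 20% TGB, 10% TGA | 54.9 → 59.4 (+4.5) | 68.4 → 70.2 (+1.8) | 0.640 → 0.678 |
| 10% TGB, 20% TGA | 55.9 → 58.1 (+2.2) | 67.9 → 71.2 (+3.3) | 0.666 → 0.631 |

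The unequal rows follow from the mechanism: extra event-free time dilutes the apparent hazard most in the arm with more scan-stoppers. The HR shifts are 0.678 − 0.640 = +0.038 and 0.631 − 0.666 = −0.035.

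**5. Adding new therapy before progression.** These are separate control-arm runs in which 15% stop and no progression is captured after new therapy. If the 15% stop imaging only and new therapy starts at 0.6% per month, the gap is up to 6.7 points. If the same 15% leave the study altogether, so that contact ends with imaging, it is up to 1.6 points without new therapy and up to 4.5 points at 0.6% per month.

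**The case against.** The best defence is that this is a stray OS sentence and not a chosen PFS rule. The bullet opens with all primary and secondary endpoints, which include OS. The wording nearly matches 7.3.2.3. The SAP 10.2 log for Amendment 1 says "Section 7.3.2.3 and Section 7.6 were updated to clarify the censoring rules for overall survival". Tables 10 and 11 leave event-free participants alone, and Protocol 10.4.1.6 has no such rule. This is probably how the sentence arose. It does not cure the text: the sentence follows directly on one about PFS and DOR and leads into two PFS tables, so a programmer would apply it there.

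Four other points stand and limit the finding.
- The analyses are optional, although SAP Appendix A lists tables for PFS with changed censoring and for DOR sensitivity.
- A reader might infer that nothing can be known about progression after new therapy. The documents do not support that. Protocol 6.6.10.1, 7.1.1.2 and 7.1.1.3 have response outcomes on new therapy recorded, and SAP Appendix A plans a figure of PFS on next treatment. What stops is the required scan.
- The documents give 15% only as a dropout rate, not as a rate of stopping imaging while staying in contact. Under Protocol 7.1.1.4 and 7.3, contact largely ends for participants who withdraw consent or cannot be reached.
- Scan-date censoring is not exact either. In the main simulation the generating 24.5-month values are 54.3% (TGB) and 67.2% (TGA). With equal shares, scan-date estimates were 0 to 1.7 points above these, and last-known-alive estimates 1.7 to 5.4 points above. In the control-arm runs with new therapy, scan-date estimates (52.5% to 54.5%) fell below the true 55.0%. The whole gap between the rules is therefore not overstatement.

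**Conclusion.** The point holds as an error in the text of an optional sensitivity analysis. SAP 7.6 as written gives the EMA-type PFS and DOR analyses a censoring date that contradicts Table 6, SAP 7.4.4 and the one-row changes in Tables 10 and 11. Followed literally, it confounds the handling of new therapy with the censoring date and inflates PFS and DOR for those who leave scanning but stay in survival follow-up. The main exposure is the Table 11 analysis.

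The effect on 24-month PFS runs from about 0.3 points with scans on schedule, through about 2 points at 10% per arm, to 4 to 5 points at 25%. Larger values arise only if new therapy before progression is added. All of this rests on assumed shares; the documents supply none. DOR was not simulated, so for DOR only the direction is argued.

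Three stronger readings are tempting and not supported:
- That the primary result is compromised. Table 6 governs the primary PFS test, and the hierarchy is untouched.
- That the rule favours tafasitamab. With equal shares the HR hardly moves, and with a 10-point imbalance it moves about 0.035 to 0.04 towards or away from 1, depending on which arm loses more scans.
- That participants starting new therapy are carried as progression-free in both analyses. In Table 10 they are events.

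**What to change.** In SAP 7.6:
- Restrict the last-known-alive sentence to OS, or move it to 7.3.2.3.
- State that in the Table 10 and Table 11 PFS and DOR analyses, participants without an event are censored at the last adequate tumor assessment, as in Table 6. For Table 11, include any adequate assessments available after new therapy starts.
- Add a row for event-free participants to both tables.
- For Table 11, say in a phrase how progression after new therapy is ascertained, since required scans have ended by then.

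The cost is a sentence or two and one row in each of two tables, with no new data and no change to the primary analysis. It should be settled before the sensitivity tables are programmed.
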